Project title: Psychoeducation for patients with bipolar disorder

NCT number: not yet assigned

Study ID: AUUR2020DKRW

Date: The 3rd of December 2020

Document type: The study protocol

Project Protocol

Psychoeducation for patients with Bipolar Disorders in Rwanda

Project background

Mental health and neurological disorders constitute 13% of the global burden of disease(1). Alarmingly this burden has risen by 41% in the last 20 years(2). In 2016, 18.5 million years were lost to disability due to mental health problems in the African region. In comparison, the disease burden of infectious and parasitic diseases in Africa was 13.1 million years lost to disability that same year(3). Currently, three out of four people with mental health problems live in low- and middle- income countries, where fewer than 1 in 50 people with severe mental disorders receive evidence-based treatment and in most countries less than 1% of the annual health budgets is allocated to mental health(4–6). The situation has been called both a failure of humanity and one of the most neglected global health issues of our time by some of the leading experts within the field of global health(7).

Bipolar disorder (BD) is characterized by periodic episodes of elevated moods and depression, which co-occur with changes in activity or energy and is associated with cognitive, physical, and behavioural symptoms(8).

It is estimated that severe mental disorders (i.e. severe depression, BD, schizophrenia and other psychotic disorders) have a two to three times higher average mortality compared to the general population(9). Treatment rates for these disorders are low in low-and-middle-income countries (LMICs), where treatment gaps of more than 90% have been documented(10,11). This might explain why a considerable proportion – up to 50% - of individuals seeking care for mental disorders in Africa consult traditional and religious healers in their pathway to mental health care(12).

One of the major barriers in decreasing the treatment gap is the lack of human resources. In response to the shortage of health professionals, experts and WHO advocate that mental health care must therefore be delegated to non-specialist health workers, who are trained to deliver interventions for specific mental disorders(13,14).

In Rwanda, a Sub-Saharan country the size of Jutland and with around 12 million citizens, the total number of medical doctors specialized in mental health is 13 in the year of 2019. So far, no treatment guidelines on mental health disorders including BD exist in Rwanda. To date, there is no data on incidence, prevalence or prognosis for BD in Rwanda.

Rwanda's health care system is organized along the principles of the WHO on primary health care(15,16). Health Centres are the first point of contact for patients. These centres also coordinate all outreach and prevention activities held at the community level, carried out by Community Health Workers (CHWs). The next level of care is the 41 District Hospitals, which has a mental health department staffed by a permanent team of psychiatric nurses and a psychologist. At the top of the mental health care system there are two national referral hospitals. The Neuropsychiatric Hospital of Ndera and the Mental Health Department of Kigali Teaching Hospital (CHUK), where only Ndera Hospital provides inpatient care. Statistics from the 2017 annual report at Ndera Hospital and CHUK shows that the annual numbers of outpatient visits with a diagnosis of BD were 1710 and 700, respectively. No data on BD is available on district or community level.

The efficacy of psychoeducation as an add-on treatment to pharmacotherapy is well documented in the treatment of symptoms and in relapse prevention initiatives with respect to BD in western countries(17). Psychoeducation is believed to empower the patient to take an active role in the therapeutic process, thereby potentially reducing stigma, guilt, and

helplessness, as well as improving medical adherence and to engage caregivers(18). Yet, no studies on psychosocial interventions for BD have been conducted in a low-income country(19).

In September 2014, the outpatient clinic of the Mental Health Department of Kigali Teaching Hospital launched a psychoeducation program for BD. The manual for the program is entitled “Life Goals Program” (LGP) and was designed back in 1996 by Bauer and McBride(20). LGP is a manual-based structured group psychotherapy program centered on behavioural principles from social education and self-regulation philosophies. Nevertheless, the effect of the psychoeducation in Rwanda is unexplored and psychoeducation is not part of the standard treatment.

Given the enormous shortage of skilled mental health professionals in Rwanda the question that emerges is whether simple interventions such as psychoeducation could potentially be decentralized from the referral hospitals and be at least as effective and acceptable as those delivered by specialist health workers at the referral hospitals.

Project aim

The overall aim of the project is to determine the effect, feasibility and acceptability of psychoeducation for patients with BD in Rwanda at district level and referral-hospital level. Moreover, the study will explore current knowledge and practice of caregiving for individuals with BD among care providers in Rwanda.

Objectives and hypothesis

Specific objective 1: To collect descriptive data on inpatients at the only inpatient neuropsychiatric hospital in Rwanda as well as to collect data on the number of patients with BD receiving outpatient care at the referral hospitals in Rwanda. This descriptive information is crucial for understanding the service provision at the referral hospitals and the accessibility to intensive mental health care in Rwanda for patients with BD.

Hypothesis 1: We hypothesise that admission data and outpatient data will demonstrate a considerable unmet need for mental health in Rwanda.

Specific objective 2: To determine the feasibility, acceptability and effect of manual-based psychoeducation for patients with BD at the two national referral and teaching hospitals in Rwanda.

Hypothesis 2: We hypothesise that the psychoeducation at the top level of mental health care for patients with BD will improve outcomes.

Specific objective 3: To determine whether the establishment of a psychoeducation program for patients with BD at district level facilitated by district nurses, will be feasible and will show the same change over time as the psychoeducation provided by staff at hospital level.

Hypothesis 3: We hypothesise that psychoeducation conducted by district mental health nurses are feasible and will have a positive effect on patient outcome.

Specific Objective 4: To explore the perceptions and experiences with the mental health

system among patients with BD as well as their relatives to obtain information that can identify different treatment practices, and their efficacy including the use of traditional healers.

Hypothesis 4: We hypothesise that patients with BD may have sought help other places than in the health care system for reasons like accessibility, stigma and culture. Moreover, we assume that they did not receive formal and evidence-based treatment before reaching the tertiary level of the health system and that the use of psychosocial interventions was limited.

Specific Objective 5: To assess the experience, knowledge and practice of caregiving for individuals with BD among traditional and alternative healers (TAH), community health workers (CHWs) as well as the mental health nurses at the district hospital. The assessment will contribute to an understanding of the feasibility of providing treatment for patients at the district and community level.

Hypothesis 5: We hypothesise that TAH as well as religious leaders are willing to collaborate with the formal health system. Moreover, we hypothesise that the CHWs and nurses want to provide evidence-based care including psychoeducation for patients with bipolar disorder but may lack the knowledge and skills

Relevance

[figure not shown]
Facing the enormous treatment gap for mental health as well as the tremendous lack of human resources for health, there is an urgent need for evidence-based operationally well-documented innovations that are compatible with the realities at a population level in resource-constrained settings. Only a very limited number of studies in low- and middle-income countries have been conducted on severe mental disorders. This project is essentially this quest. Potential positive outcomes may be effected not just in Rwanda, but also in similar low-resource settings elsewhere. If proven successful, relevant next steps will include having the newly established research group expand its focus area to severe mental health disorders other than BD; or to conduct studies on the drug treatment of BD in low-income settings. Moreover, the project will serve to enhance local research capacity.

Study design

The study consists of a **quantitative part** and a **qualitative part**.

The quantitative part is divided into a prospective randomized controlled trial (RCT), and a district trial (Figure 1)

Figure 1: Project division

* A psychiatric nurse and either a psychologist or a psychiatric resident will conduct the psychoeducation.

** Two district mental health nurses will conduct the psychoeducation

— RCT

----The district trial

Participants

Inclusion criteria: A diagnosis of BD type I or II that meets DSM-V diagnostic criteria given by a trained psychiatrist and no episode in the preceding 4 weeks. Age ≥ 18 years.

Exclusion criteria: Exclusion criteria will be applied to obtain a sample reflecting the general patient population. The exclusion criteria include: Previous participation in any structured psychological intervention, such as psychoeducation or cognitive remediation, mental retardation, insufficient understanding of Kinyarwanda or deafness, alcohol or drug-dependence.

Intervention groups:

The RCT: Outpatients from the two-referral hospitals in Rwanda will be invited to participate and be allocated to intervention group or control group.

Intervention-arm: Manual-structured group psychoeducation. LGP is organized in two phases. Phase 1 of the LGP psychoeducation is mandatory and entails 8 sessions of 90 minutes over the course of 8 weeks (at one session per week) and has shown effect in western countries(21–23). Phase 2 will be offered after study completion. All groups will have 6-8 participants and two health professionals to conduct the sessions; a psychiatric nurse and either a psychologist or a psychiatric resident. Patients will be offered to invite their relatives for 2-3 psychoeducation-days for relatives.

Control group: Participants in the control group will be assigned to a waiting list and receive group-psychoeducation after the active intervention groups.

The district trial: This trial compares the impact of psychoeducation given at district level by district mental health nurses with the psychoeducation conducted at referral hospital (arm 1)

Randomization:

Study participants at the hospital level who meet the inclusion criteria and sign the informed consent form will be randomized individually into either intervention-arm or waiting list through block-randomization with a ratio of 1:1.

Patients at district level will not be randomized since we are unsure of the number of patients with BD at these levels fearing that the sample size will be too small. Instead all will be offered participation.

Outcome assessments:

All outcomes will be assessed at baseline, immediately post-intervention and at the 3rd and 6th month follow-up. The outcomes are based on the most commonly used measurements for trials on psychoeducation for individuals with BD in high and middle-income countries(18,19)

Baseline data: The Mini-International Neuropsychiatric Interview(24) will be used to confirm psychiatric diagnosis. Demographic information regarding the participants' living circumstances, past psychiatric history and mental health service use data will also be collected from interviews and patient files.

Primary outcomes: Relapse is defined as a new mood episode of mania (scores above or equal to 20 on the Young Mania Rating Scale (YMRS)(25)), hypomania (above or equal to 12 on the YMRS), or depression (above or equal to 17 on the Hamilton Depression Scale-17(HDRS-17(26)) or mixed episode (above or equal to 20 on the YMRS and 12 on the HDRS-17).

Secondary outcomes: The Clinical Global Impression (CGI-I /CGI-S) will be used for the clinicians to assess how much the participant's condition has improved. The Medication Adherence Rating scale (MARS) will be used to assess the adherence. All participants will fill in questions about self-stigma before and after the psychoeducation.

Tertiary outcomes: A seven-item questionnaire based on The theoretical framework of acceptability(27) will be used to access the acceptability of the intervention.

The Young Mania Rating Scale and The Medication Adherence Rating scale both needs to be cultural adapted and validated using a forward–backward translation, consensus conference and cognitive interviews (approx. 15).

Sample size:

In the literature on group-psychoeducation, 13 out of 18 RCT's have reduction in general psychiatric symptom severity, incidence of relapse and hospitalization as main outcomes(18). We reviewed 18 RCT's on group psychoeducation for BD before we selected a study of Colom et al. as the base of our power calculation(18,28). The incidence of relapse in the study was (92%) (55 subjects) in the control group vs. 67% (40 subjects) in the psychoeducation group. For our study a sample size of 40 patients for each arm is required to achieve a level of 80% power with a 5% level of significance, when comparing the mean change in each intervention with the control arm via a two-sample t-test. Adjusting for a drop-out rate of 20%: $40/(1-(20/100)) = 50$ participants will be needed for each group.

Finally, for a one-year period, descriptive data on all inpatients with age > 18 years, discharged from Ndera the only inpatient psychiatric hospital, will be collected from files.

The qualitative part consists of three substudies. Each of the three substudies and their corresponding research question is outlined in Table 1, and the methodological approaches are described in further details in the following sections.

Table 1. Qualitative part

| # | Substudy | Research question | Empirical data | Methods |
|-------------------------|----------|---|--|----------------------|
| 1 Patients | | What is the living experience of adults with bipolar disorder in Rwanda? | Semi-structured interviews (approx. 10-20) | Qualitative analysis |
| 2 Relatives | | How do relatives experience the mental health service system? What is the impact of caregiving on the caregiver and their living experience? | Semi-structured interviews (approx. 10-15) | Qualitative analysis |
| 3 Care providers | | What knowledge, experience and practice of caregiving for individuals with BD do health providers in Rwanda have? Are TAH and religious leaders willing to collaborate with the formal health system? | Focus groups (approx. 4) | Qualitative analysis |

Semi-structured qualitative interviews with patients will be conducted using the methodological framework of phenomenology to explore their personal use and experiences of mental health care in Rwanda. Patients will be recruited from the group-psychoeducation program. Patients' relatives who sign up for psychoeducation-days for relatives will be asked if they want to participate in a semi-structured qualitative interview on the burden of caregiving.

Focus groups will also be conducted with CHWs as well as mental health nurses at different district hospitals and TAH and religious leaders. The interviews will be transcribed in their full length. Data will be analysed to explore the experience, knowledge and practice of treatment provided at district- and community level for patients with Bipolar Disorder.

Ethical Approval

The research protocol and study-related documents will be presented to the Rwandan National Ethical Committee (RNEC) for approval prior to study initiation. Informed consent will be obtained from participants after oral and written information.

A “twin model PhD project”:

[figure not shown]
To ensure general capacity building extending further than our research team, we collaborate with a local partner institution in Rwanda – University of Rwanda. Furthermore, this research will be a ‘twin model’ PhD project(29) involving two PhD-students: [name] - a Rwandese psychiatrist and [name] – a Danish doctor. The twin model is based on the principles of local capacity building to ensure high scientific standards and participation by local stakeholders and prevents extractive research and scientific colonialism(29,30). This is in line with UN’s sustainable development agenda, goal 17 on partnerships (31). The project will bring together three academic institutions in a partnership: Aarhus University (AU), University of Rwanda (UR) and Copenhagen University (Competence Centre for Transcultural Psychiatry).

Segregation of duties

The different tasks and responsibilities have been divided between the two PhD-students. [name] will mainly focus on psychoeducation at the district level and the qualitative part of the study (objective 3-4-5). [name] will be

responsible for the RCT and the data collection at the referral hospitals (objective 1-2). Figure 2 illustrates “The Twin PhD model” including the shared tasks and the division of responsibilities.

Figure 2: Twin-PhD-model and the segregation of duties

Feasibility

The intervention chosen – The Life Goal Programme (LGP) – is already adapted and used in a Rwandan setting. Moreover, statistics from the 2017 annual report from the two referral hospitals show that the annual numbers of outpatient visits with a diagnosis of BD were 1710 and 700 respectively, making it highly possible to include the required 150 participants from the referral hospitals. The research team is an interdisciplinary team comprised of professionals within the field of public health, transcultural psychiatry and psychology. The Rwandan PhD applicant holds professional experience in treating mental health patients in Rwanda as a trained psychiatrist; while the Danish PhD applicant has experience from DANIDA-related partnership projects in Rwanda.

Research plan and timetable

Our planned activities for the three-year project, starting in November of 2019, are presented in Table 2. We aim to initiate data-collection in the Summer of 2020.

Table 2. Activities of the three-year project.

| Research activities | Year 1 | | | | Year 2 | | | | Year 3 | | | |
|--|--------|----|----|----|--------|----|----|----|--------|----|----|----|
| | Q1 | Q2 | Q3 | Q4 | Q1 | Q2 | Q3 | Q4 | Q1 | Q2 | Q3 | Q4 |
| Development of the protocol and study related documents – applying for RNEC ethical approval | | | | | | | | | | | | |
| Validate tools (YMRS and MARS) | | | | | | | | | | | | |
| Development of focus-group questionnaire for caregivers | | | | | | | | | | | | |
| Screening and enrolment of study participants for psychoeducation | | | | | | | | | | | | |
| Follow-up | | | | | | | | | | | | |
| Data collection on inpatients | | | | | | | | | | | | |
| Data cleaning and analysis | | | | | | | | | | | | |
| Authoring manuscripts | | | | | | | | | | | | |
| Authoring dissertation | | | | | | | | | | | | |

Dissemination of research results

The project aims at directing research and policy attention towards mental health at the global, national and local level. For the dissemination of the outcomes of the project, we will: a) publish articles in scientific journals; b) present results at international scientific meetings and conferences; c) organise local meetings with key stakeholders during the full extent of the project.

Publications

The research project will result in several planned publications:

1. *A descriptive analysis of inpatients with mental health disorders in Rwanda*
2. *A randomized trial on the efficacy of group psychoeducation on recurrence, self-stigma and medication adherence in individuals with bipolar disorder in Rwanda*
3. *Caregiver burden in bipolar disorder: A study from Rwanda*
4. *Feasibility and impact of group psycho-education at district level on quality of life, recurrence, self-stigma and medication adherence in individuals with bipolar disorder in Rwanda*
5. *Knowledge, practices and attitudes towards bipolar disorder among traditional and religious healers in Rwanda.*
6. *Mental health professionals' perceptions of the use of traditional and alternative medicine in the care for patients with bipolar disorder in Rwanda.*
7. *Rwandan traditional and religious healers' perceptions towards western medicine.*
8. *Pathways to psychiatric care and treatment of patients with bipolar disorder in Rwanda.*

References

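### Objective 3 asks whether district delivery gives the same change as hospital delivery, but an unrandomised district group set against treated arm 1, with no sample size for that contrast, cannot show it; the 150 for the referral hospitals also conflicts with two arms of 50

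*Protocol*

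**What the plan says.** Specific objective 3 (Objectives and hypothesis) has two parts: whether a nurse-led district programme is feasible, and whether it "will show the same change over time as the psychoeducation provided by staff at hospital level". Hypothesis 3 expects that district sessions "are feasible and will have a positive effect on patient outcome". The question that closes the Project background is whether decentralised delivery could "be at least as effective and acceptable as those delivered by specialist health workers at the referral hospitals". The Project aim also lists effect at district level among the things to be determined.

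The district trial paragraph (Intervention groups) compares the impact of district delivery with that of arm 1, the referral-hospital group that receives psychoeducation. Under Randomization: "Patients at district level will not be randomized since we are unsure of the number of patients with BD at these levels". Everyone at district level is offered the programme instead. The hospital trial has two arms at 1:1, psychoeducation and waiting list.

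The Sample size section gives one calculation. It takes relapse of 92% (control) and 67% (psychoeducation) from a cited trial and arrives at 40 per arm for 80% power at the 5% level, "when comparing the mean change in each intervention with the control arm via a two-sample t-test". After 20% dropout, 50 "participants will be needed for each group". The Feasibility section then puts the number required from the referral hospitals at 150.

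**The concern.** Objective 3 and the background question are claims of sameness or non-inferiority. The design that should support them is a non-randomised comparison with a treated group, and the stated sample size concerns a different contrast. If the difference turned out small or non-significant, the data could not separate equal benefit from a substantial loss of benefit, or either of these from differences in who attends and who delivers. The protocol presents moving care to district level as the practical question, so what this comparison can support matters. The feasibility part of Objective 3 and Hypothesis 3 is not affected.

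The count of 150 is a smaller inconsistency, but it bears on the same issue: it leaves unclear how many groups the calculation was meant to serve.

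**Working it through.** **1. The plan's own figure.** Inputs from Sample size: 0.92 v 0.67, 5% level, 80% power. Sidedness is not stated; two-sided is assumed because it returns the printed number. Two proportions, pooled variance under the null, mean proportion 0.795:

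n = [1.96 × √(2 × 0.795 × 0.205) + 0.842 × √(0.92 × 0.08 + 0.67 × 0.33)]² / 0.25² = 39.7, so 40 per arm. Dropout: 40 / 0.8 = 50. Both reproduce.

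**2. Which contrast this covers.** It is a test for a difference between an intervention and the control arm. The district trial paragraph names a different contrast, district v arm 1, with both groups treated. The hospital trial has only one intervention arm, yet the sentence speaks of each intervention, so the district group may have been meant to be set against the waiting list. Even then, district v arm 1 is not sized.

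**3. Precision of district v arm 1 (illustrative).** Assumptions: 67% relapse in both groups, 40 or 50 per group. Half-width = 1.96 × √(0.67 × 0.33 × (1/n₁ + 1/n₂)).

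- 40 v 40: 1.96 × 0.105 = 20.6 points.
- 50 v 50: 1.96 × 0.094 = 18.4 points.
- Relapse of 50% in both: 21.9 and 19.6 points. Relapse of 80%: 17.5 and 15.7 points.
- Arm 1 at 40, district number varied: 25.2 points with 20 district patients, 22.3 with 30, 18.8 with 60, 17.2 with 100.

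The assumed benefit is 92 − 67 = 25 points.

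**4. Non-inferiority (illustrative margins; one-sided 2.5%, 80% power, no true difference).** n per group = (1.96 + 0.842)² × 2 × 0.67 × 0.33 / margin².

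- Margin of half the benefit (12.5 points): 222.1, so 223 per group, or 223 / 0.8 = 279 with dropout.
- Margin of the whole benefit (25 points): 55.5, so 56 per group, or 70 with dropout.
- Power at 40 v 40 is Φ(margin / 0.105 − 1.96): 22% at 12.5 points and 66% at 25 points.

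**5. How little a non-significant result says.** Suppose district delivery lost half the benefit, so relapse were 67 + 12.5 = 79.5%. At 40 v 40 the standard error is √((0.67 × 0.33 + 0.795 × 0.205) / 40) = 0.098, and power is Φ(0.125 / 0.098 − 1.96) = 25%. A two-sided 5% test would be non-significant about 75% of the time, and about 70% at 50 v 50.

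**6. The same on a mean-change scale.** Objective 3 speaks of change, and the stated test is a t-test. With 40 per group, that test has 80% power for a difference of about 0.63 SD. The 95% half-width is 1.96 × √(2/40) = 0.44 SD (0.39 SD at 50 v 50). A non-inferiority margin of 0.3 SD, about half of 0.63, needs 2 × (2.802 / 0.3)² = 174.5, so 175 per group. The picture does not depend on the choice of scale.

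**7. Head count.** Two hospital arms: 2 × 50 = 100. The stated 150 equals 3 × 50, but a third group of district patients would not come from the referral hospitals.

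**The case against.** - **Control for the district effect.** A reader might infer that any district effect would rest solely on uncontrolled change from baseline. The text does not settle this. If each intervention in Sample size includes the district group, there would be a comparison with the waiting list, and a total of 150 fits that reading. The background says "there is no data on incidence, prevalence or prognosis for BD in Rwanda", but the waiting list would itself supply concurrent data on untreated course, at least until it is offered the programme. This stands. What remains is that such a comparison is not randomised: the controls are referral-hospital patients, so it is confounded.
- **Reading non-significance as sameness.** A reader might infer that the authors intend this. No passage gives a decision rule for Objective 3, and a margin or adjustment may sit in an SAP that is not shown. So neither intent nor a missing margin is the finding. But an SAP cannot supply randomisation, and adjustment reduces confounding by site without removing it.
- **Candour in the protocol.** It gives its reason for not randomising, and the list of planned publications describes the district paper as feasibility and impact. Hypothesis 3 claims no sameness. This is fair, but Objective 3 still promises to determine sameness.
- **The magnitudes.** They rest on relapse rates from one cited trial and assumed district numbers. This stands; they are illustrations, and ranges are given.
- **The 150.** It appears once and may be a three-group total loosely worded. Figure 1, which shows the project division, is not reproduced. The 150 therefore shows a contradiction to reconcile, not that recruitment will go wrong by 50.

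**Conclusion.** The point holds for Objective 3 and Hypothesis 3 as worded. A non-randomised comparison with treated arm 1 cannot determine that the change is the same, and the only sample size does not address that contrast. With an assumed 40 to 50 per group and 67% relapse in both, the uncertainty (about 18 to 21 points either side) is nearly as large as the whole assumed benefit of 25 points; non-inferiority at half that benefit would need about 223 evaluable per group. Confounding by site, staff and patient mix comes on top of this imprecision.

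The positive effect in Hypothesis 3 has no randomised comparator, whether it is judged by change from baseline or against the hospital waiting list. The 150 contradicts the 100 that follows from the stated arms.

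The documents do not support going further and saying that the district group has no control of any kind, or that the calculation was certainly meant for the randomised comparison alone.

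**What to change.** 1. Reword Objective 3, for example: *To assess the feasibility and acceptability of psychoeducation delivered by district nurses and, as an exploratory analysis, to estimate with 95% confidence intervals the difference between district patients and arm 1 in relapse and in the secondary outcomes.* Adjust for the baseline score where an outcome has one. For relapse, adjust for baseline characteristics, since entry requires four weeks without an episode and there is no baseline value; the covariate list can go in the SAP. State that residual confounding by site remains and that a non-significant difference will not be taken as sameness. Bring the district effect wording in the Project aim and the impact wording in the district trial paragraph into line.
2. Limit Hypothesis 3 to feasibility and acceptability, or label its effect as exploratory and non-randomised.
3. Reconcile the Intervention groups, Sample size and Feasibility sections. Say which contrasts each intervention covers, state that district v arm 1 is not powered, and replace 150 by 100 from the referral hospitals plus the planned district number.

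The cost is a more modest district claim and slightly more analysis work, with no extra patients, visits or measurements. Powering a non-inferiority claim instead looks out of reach, since the protocol already fears too few district patients.

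### The 40 evaluable per arm for 80% power assumes independent patients, although the intervention arm is treated in groups of 6-8 with shared facilitators

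*Protocol*

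**What the plan says.** Under Randomization, eligible patients at the referral hospitals "will be randomized individually into either intervention-arm or waiting list", 1:1. Under Intervention groups, the intervention is eight weekly group sessions, and "All groups will have 6-8 participants and two health professionals to conduct the sessions". The footnote to Figure 1 describes the facilitators: "A psychiatric nurse and either a psychologist or a psychiatric resident will conduct the psychoeducation". Controls wait and "receive group-psychoeducation after the active intervention groups". Outcomes are assessed at baseline, "immediately post-intervention and at the 3rd and 6th month follow-up".

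Under Sample size, the basis is a published trial: "The incidence of relapse in the study was (92%) (55 subjects) in the control group vs. 67% (40 subjects) in the psychoeducation group". The protocol then states that "a sample size of 40 patients for each arm is required to achieve a level of 80% power with a 5% level of significance", for a comparison of mean change by two-sample t-test. One inflation follows, "Adjusting for a drop-out rate of 20" per cent, which takes 40 to 50 per group. No ICC, design effect or statement about independence appears. Under Feasibility, the number required from the referral hospitals is given as 150.

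**The concern.** Patients who attend the same eight sessions with the same peers and the same two facilitators may have correlated outcomes. Individual randomisation does not prevent this, because the correlation arises after allocation. Waiting-list controls share no group until they are treated, so the clustering lies in one arm only.

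Two things are at stake. First, positive correlation raises the variance of the intervention-arm estimate, so a power computed for independent patients is too high. An analysis plan can correct the standard error later, but it cannot restore power that the sample size did not provide. Second, an ordinary two-sample test that ignores the grouping would reject too often under the null.

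**Working it through.** **Inputs.** From the protocol: relapse 92% (control) and 67% (psychoeducation), 40 evaluable per arm, 5% level, 20% drop-out, groups of 6-8. Assumed, because the protocol does not say: a two-sided test; ICC 0, 0.01, 0.02, 0.05 or 0.10 in the intervention arm only; uncorrelated controls.

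**1. Reproducing the 40.** Mean rate = (0.92 + 0.67)/2 = 0.795.
- SE0 = sqrt(0.795 × 0.205 × 2/40) = 0.0903
- SE1 = sqrt((0.92 × 0.08 + 0.67 × 0.33)/40) = 0.0858
- Pooled power = Phi((0.25 − 1.96 × 0.0903)/0.0858) = 80.3%

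At 39 per arm it is 79.2%, so 40 is the smallest number that reaches 80%; 40/0.8 = 50. Other forms give other numbers: 38 unpooled, 48 with continuity correction, 32 one-sided. The origin is therefore very likely rather than certain, but every one of these forms treats patients as independent.

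**2. Groups.** 50/8 = 6.25 and 50/6 = 8.33, so 50 patients form 7 or 8 groups. Evaluable patients per group: m = 40/7 = 5.71 or 40/8 = 5.0. Design effect in the intervention arm: DE = 1 + (m − 1) × ICC.

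**3. Power with clustering in one arm.**
- SE0 = sqrt(0.795 × 0.205 × (1 + DE)/40)
- SE1 = sqrt((0.0736 + 0.2211 × DE)/40)
- Pooled power = Phi((0.25 − 1.96 × SE0)/SE1)
- Unpooled power = Phi(0.25/SE1 − 1.96)

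Example, ICC 0.05 and 7 groups: DE = 1 + 4.71 × 0.05 = 1.236, SE0 = 0.0954, SE1 = 0.0931. Pooled power is Phi(0.677) = 75.0%; unpooled is Phi(0.725) = 76.6%.

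The last column is the actual power of the pooled test with the design effect treated as known: exact binomial enumeration at ICC 0, beta-binomial simulation otherwise.

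| ICC | DE | Effective n, intervention | Pooled formula | Unpooled formula | Pooled test, exact or simulated |
|---|---|---|---|---|---|
| 0 | 1.00 | 40 | 80.3% | 83.0% | 82.8% |
| 0.01 | 1.04-1.05 | 38 | 79.2-79.4% | 81.7-81.9% | 82.4% |
| 0.02 | 1.08-1.09 | 37 | 78.1-78.4% | 80.4-80.8% | 80-82% |
| 0.05 | 1.20-1.24 | 32-33 | 75.0-75.8% | 76.6-77.5% | 77.5-78.5% |
| 0.10 | 1.40-1.47 | 27-29 | 70.3-71.7% | 70.7-72.4% | 73-73.5% |

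The pooled formula understates the power of its own test at ICC 0 by 2.5 points (80.3% against 82.8%). At low ICC the other two columns are therefore the better guide: 82-83% at ICC 0-0.01 and 80-82% at 0.02. At 0.05 and 0.10 the three methods together span about 75-78% and 70-74%.

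**4. Cross-check on the named t-test.** No mean difference or SD is given. For means, 40 per arm and 80% power correspond to a standardised difference of about 0.63. With 4.8-5.6 evaluable per group, power is then about 76% at ICC 0.05 and 71-73% at 0.10, so the conclusion does not depend on which endpoint scale was meant.

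**5. Type I error if grouping is ignored.** 2 × (1 − Phi(1.96/sqrt((1 + DE)/2))). For DE = 1.236: sqrt(1.118) = 1.057, 1.96/1.057 = 1.854, giving 6.4%. Over 7-8 groups the formula gives 6.2-6.4% at ICC 0.05 and 7.4-7.8% at 0.10. Allowing for simulation of the binary outcome, about 6.3-6.5% and 7.5-8% are fair figures.

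**6. If the total is 150.** 75 per arm gives 75 × 0.8 = 60 evaluable in 10-12 groups, so m = 6 or 5. The pooled formula then gives 90-91% at ICC 0.05 and 86-88% at 0.10. No shortfall remains at these values.

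**The case against.** **Two stronger readings are tempting, and neither is supported.** A reader might infer from the pooled formula that the design has almost no room for correlation, since that formula falls to 80% at an ICC of about 0.003. This is mostly an artefact of the approximation: by simulation 80% holds to about ICC 0.02, and by the unpooled formula to 0.023-0.027. A reader might also put the shortfall at the level given by a group-level test with Satterthwaite degrees of freedom, 67-70% at ICC 0.05 and 61-64% at 0.10. That test is conservative and the protocol does not name it. It gives 75-76% even at ICC 0, which cannot be a clustering defect of the plan. Small-sample degrees of freedom do cost something, but how much depends on the method chosen.

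**The ICC is assumed.** Nothing in the documents favours 0.05 over 0.01, and at 0.01 the loss is negligible. This stands. It means the material supports a sensitivity statement, not a demonstrated shortfall.

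**The model belongs in the statistical analysis plan.** Largely true. That plan is not at hand, and the type I error figures apply only if an unadjusted test is used. The sample size and its flat 80% are stated in the protocol, however, and identifiers not collected during the trial cannot be modelled later.

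**The basis is itself unclear.** The section quotes relapse proportions but names a t-test on mean change, and 100 does not agree with 150. Both are separate matters, and the second decides whether any shortfall exists. Neither shows that clustering was considered.

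**Limits of the calculation.** The protocol does not say whether controls start their own groups before month 3 or month 6; if they do, one-arm clustering no longer describes those visits. If patients cannot share groups across the two hospitals, the group count may also differ.

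**Conclusion.** The point holds in a limited form. The stated 80% power at 40 evaluable per arm rests on independent patients, in a design that treats one arm in small groups with shared facilitators, and only drop-out is allowed for. The effect is negligible at ICC 0.01. At ICC 0.05 power falls about 2 to 5 points below the stated 80%, and at 0.10 about 6 to 10 points, with a little more lost once the ICC is estimated with small-sample degrees of freedom.

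These sizes assume 92% against 67% relapse, 7-8 groups, 20% drop-out, ungrouped controls and 50 randomised per arm. If 75 per arm is intended, the shortfall disappears over this ICC range, leaving only the unstated assumption and the choice of analysis. The point merits correction but does not invalidate the design.

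**What to change.** 1. Reconcile the two arms of 50 under Sample size with the 150 under Feasibility, and state how many are randomised per arm. Do this first, because it determines whether power needs further attention.
2. Under Sample size, say that 80% assumes independent patients. Give power for the relapse comparison over a stated ICC range, using one named method for ICC 0 and all other values, including any degrees-of-freedom correction.
3. Record psychoeducation group and facilitator pair for every treated patient.
4. In the protocol or the statistical analysis plan, replace the plain two-sample comparison with a partially nested model: a group effect in the intervention arm only, at visits before controls receive group psychoeducation, with the small-sample method named. State when controls start relative to the month 3 and month 6 visits.

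The cost is protocol wording, two recorded identifiers and a less favourable stated power. Before any degrees-of-freedom correction, intervals widen by about 5-11% at ICC 0.05-0.10 with equal arm variances, or 7-16% at 92% against 67% relapse. No patients need be added if the lower power is accepted.
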